#### **7.1.8 Corneal confocal microscopy (only for patients who underwent LASIK surgery)**

In vivo scanning confocal microscopy will be performed bilaterally in the central cornea to more closely examine the corneal epithelium, sub-basal nerve plexus, stroma and endothelium with particular attention given to the presence and density of corneal nerves. Prior to the procedure patients will be treated with anesthetic drops and a viscoelastic liquid gel will be applied to the cornea as an immersion substance for the microscope lens.

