### **5.2 Inclusion criteria**

To be enrolled in this study, patients must fulfil all these criteria:

1. Male or female  $\geq 18$  years old
2. Patients who are characterized by the following clinical features:
  - a. History of cataract or refractive corneal surgery in the study eye(s) in the previous 6 months;
  - b. Mean Symptom Assessment in Dry Eye (SANDE) score for severity and frequency of at least 30 at baseline
3. The same eye (study eye) must fulfill all the above criteria
4. Best corrected distance visual acuity (BCDVA) score of  $\geq 0.1$  decimal units in both eyes at the time of study enrolment
5. Female patients must have negative pregnancy urine test if at childbirth potential.
6. Only patients who satisfy all requirements for informed consent may be included in the study. Written Informed Consent must be obtained before the initiation of any study-specific procedures.
7. Patients must have the ability and willingness to comply with study procedures.

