#### **➤ Follow-up phase**

- Week 12 Visit Follow-Up - Day 84 ± 2

	Day	Procedures/Assessments
Baseline Visit	Day 0	
 
➤ Explanation to the patient of study aims, procedures and possible risks
 
➤ Informed consent signature
 
➤ Screening number allocation (as S001, S002, etc.)
 
➤ Demographic data
 
➤ Medical and surgical history/current medical conditions
 
➤ Prior/concomitant medications
 
➤ AE monitoring
 
➤ Ocular examination of both eyes:               
 
1. Assessment by Symptom Assessment iN Dry Eye (SANDE)
 
2. Assessment of best corrected distance visual acuity (BCDVA)
 
3. Slit lamp examination (SLE) to assess the Eyelid - Meibomian glands, Eyelid – Erythema, Eyelid - Oedema Lashes, Conjunctiva Erythema, Lens, Iris, Anterior Chamber
 
4. External Ocular Examination
 
5. Corneal Confocal Microscopy (Only for patients who underwent LASIK surgery)
 
 
Ten minutes break
 
6. Tear Film Break Up Time (TFBUT)               
Five minutes break
 
7. Corneal sensitivity (Cochet-Bonnet)               
Ten minutes break
 
8. Ocular surface staining (NEI score)               
Ten minutes break
 
 
➤ Frequency of patient's own artificial tear use (to be reported in eCRF)
 
➤ Pregnancy test for female patients.
 
➤ Patient eligibility: Inclusion/exclusion criteria evaluation
 
➤ Assignment of study eye(s) (Note: if both eyes are eligible, study treatment will be administered to both eyes, and each eye will be considered as "study eye")
 
➤ Randomization
 
➤ Study Drug Dispensation
 

 
Note: At the study visit the Investigator will provide each patient with diary and one monthly box of the study drug for the following 4 weeks together with an adequate number of adaptors and syringes.
 
After visit completion patients will start topical ocular treatment as per instructions and will self-administer at home the IMP. Patients will return to the clinical site on Day 28 ± 2 (Week 4 Visit).
 
The patients will be instructed to fill in the diary with time of self-administration, potential AE occurrence, concomitant medication intake and the quantity of artificial tears used, and to return the refrigerated box on the Week 4 visit.

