At home	Days 28±2 -56±2	
 
➤ Self-administration at home of the IMP, six times daily every 2 h (diary) in every study eye
 
➤ Artificial tears use (diary)
 
➤ Recording any new or changes in concomitant medications (diary)
 
➤ Recording any unusual medical conditions - AE monitoring (diary)
 
 
Data will be recorded by the patient on the patient’s diary.

	Day	Procedures/Assessments
Week 8 Visit	Day 56±2  Or  Early termination (if applicable)	
In case of study early discontinuation (at any time) patients will undergo the assessments foreseen at Week 8 visit.
 
 
➤ Compliance to treatment (from patient diary and control of returned weekly boxes)
 
➤ current medical conditions
 
➤ concomitant medications
 
➤ AE monitoring
 
➤ Ocular examination in both eyes:               
 
1. Assessment by Symptom Assessment iN Dry Eye (SANDE)
 
2. Assessment of best corrected distance visual acuity (BCDVA)
 
3. Slit lamp examination (SLE) to assess the Eyelid - Meibomian glands, Eyelid – Erythema, Eyelid - Oedema Lashes, Conjunctiva Erythema, Lens, Iris, Anterior Chamber
 
4. External Ocular Examination
 
5. Corneal Confocal Microscopy (Only for patients who underwent LASIK surgery)
 
 
Ten minutes break
 
6. Tear Film Break Up Time (TFBUT)
 
Five minutes break
 
7. Corneal sensitivity (Cochet-Bonnet)
 
Ten minutes break
 
8. Ocular surface staining (NEI score)
 
Ten minutes break
 
 
➤ Frequency of patient’s own artificial tear use (to be reported in eCRF)
 
➤ Pregnancy test for female patients.
 
 
Note: The Investigator will deliver to the patients the diary. Patients will return to the clinical site on Day 84 ± 2 (Week 12 Visit). The patients will be instructed to fill in the diary with AE occurrence, concomitant medication intake and the quantity of artificial tears used.

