## **7 DESCRIPTION OF SPECIFIC PROCEDURES**

### **7.1 Ophthalmological Evaluations**

Ocular evaluations will be performed on both eyes even if just one eye is eligible (determined as study eye). The assessments must always be performed according the sequence detailed in Par 6.1. The assessment will be performed at Day 0 Baseline Visit, Week 4 Visit, Week 8 Visit and at Week 12 Visit. The ophthalmological assessment will include:

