### **7.1.6 Corneal sensitivity**

For the assessment of corneal sensation the Luneau Cochet-Bonnet aesthesiometer (Western Ophthalmics Corporation©) should be used.

The Cochet-Bonnet aesthesiometer contains a thin, retractable, nylon monofilament that extends up to 6 cm in length. Variable pressure can be applied to the cornea by adjusting the monofilament length. The monofilament length ranges from 6 to 0.5 cm. As the monofilament length is decreased the pressure increases from 11 mm/g to 200 mm/g.

Corneal sensation will be measured in both eyes in each of the four quadrants of the cornea using the Cochet Bonnet aesthesiometer before the instillation of any dilating or anesthetic eye drops.

Steps for using the Cochet Bonnet aesthesiometer: extend the filament of the aesthesiometer to full length of 6 cm. Slowly advance the monofilament towards the eye until the tip perpendicularly touches the corneal surface. Continue to exert a slight pressure until obtaining an inflection deviation of the filament of about 4% (i.e. the first visible inflection). If a positive reaction to the touch of cornea is elicited proceed to step 3. If a positive reaction is not achieved proceed to step 2. (NOTE: A positive response is any action indicating corneal sensation whether communicated verbally or physically).

Retract the filament incrementally in 0.5 cm and repeat this step until the patient gives a positive reaction indicating that the contact of the monofilament on the cornea has been sensed. (NOTE: The shorter filament lengths indicate decreased corneal sensation).

Record the length of the filament in cm at which the patient sensed the contact with the cornea.

Repeat steps 1-3 in each of the 4 corneal quadrants (superior nasal, inferior nasal, superior, temporal and inferior temporal) in the study eye(s) and in each of the 4 corneal quadrants of the other eye (not the study eye, if applicable).

To clean the instrument, please refer to your national standards for devices that contact the eye and tears or follow the suggested manufacturer's recommendations.

The length of the filament in cm at which the patient corneal sensation was observed for the tested area of the cornea will be entered into the eCRF.

Corneal sensitivity findings will be entered in the eCRF.

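### In LASIK patients the mandatory assessment order puts anaesthetic drops before Cochet-Bonnet aesthesiometry, which Protocol 7.1.6 requires to be done before any such drops

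*Protocol*

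**What the plan says.** Four parts of the protocol bear on this.

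- **Order.** Protocol 7.1 states: "The assessments must always be performed according the sequence detailed in Par 6.1". In the Baseline and Week 8 lists of section 6.1, step 5 is confocal microscopy (LASIK patients only), step 6 is TFBUT, step 7 is Cochet-Bonnet and step 8 is NEI ocular surface staining. The Week 8 list also serves early termination: "In case of study early discontinuation (at any time) patients will undergo the assessments foreseen at Week 8 visit".
- **Anaesthetic.** Protocol 7.1.8 states: "Prior to the procedure patients will be treated with anesthetic drops and a viscoelastic liquid gel will be applied to the cornea". Both eyes are involved: "In vivo scanning confocal microscopy will be performed bilaterally in the central cornea".
- **Condition on the sensation test.** Protocol 7.1.6 has sensation measured in both eyes, in four quadrants, "using the Cochet Bonnet aesthesiometer before the instillation of any dilating or anesthetic eye drops".
- **Use of the data.** Change in Cochet-Bonnet aesthesiometry is a secondary efficacy endpoint (Protocol 2.2), measured only at Day 0 and Week 8 (SAP 7.2.7). SAP 9.5.3 summarises it by treatment group, visit and eye, without inference.

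**The concern.** A site examining a LASIK patient cannot keep to the 6.1 order and also satisfy 7.1.6. The documents do not show which instruction the site follows.

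The trial's rationale is surgical damage to the corneal sensory nerve plexus, and Cochet-Bonnet is the only listed efficacy endpoint that measures corneal sensation directly. It is scheduled at just two visits, and the conflict arises at both, so a LASIK patient has no other scheduled reading to fall back on. Under SAP 9.5.3, readings taken after anaesthetic would be summarised together with readings from patients who had none. The SAP has no pre-specified split for them: its only subgroup is one versus two study eyes (SAP 6.2), and its definition of corneal sensitivity carries no variable for test order or anaesthetic use (SAP 7.2.7).

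**Working it through.** The plan states no figure on this point. The check is a comparison of instructions, followed by a count of the readings concerned.

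**1. Order at the visits where both tests are scheduled.** The schedule of assessments places both tests at Baseline and Week 8 only. At both, confocal microscopy (step 5) precedes Cochet-Bonnet (step 7), so the conflict occurs at 2 of 2 visits. At Week 4 and Week 12 neither test is scheduled.

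**2. Whether the breaks resolve it.** Section 6.1 has a ten-minute break after step 5 and a five-minute break after step 6: 10 + 5 = 15 minutes, plus the TFBUT test. Section 7.1.6 requires measurement before instillation, so a waiting time does not satisfy it. No passage gives a washout rule, a separate day for confocal microscopy or an exception for LASIK patients.

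**3. Whether the schedule table gives another order.** The Study Schedule lists Cochet-Bonnet above confocal microscopy. That table assigns procedures to visits. It also lists fluorescein staining above TFBUT, whereas 6.1 puts TFBUT first, so its rows are not an order of testing. Section 7.1 names 6.1 as the source of the order.

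**4. Readings concerned, per eye of a LASIK patient.** 2 visits x 4 quadrants = 8 readings, giving 4 quadrant changes from baseline.

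| Instruction followed | Readings that meet 7.1.6 | Changes from baseline |
|---|---|---|
| 6.1 at both visits | 0 of 8 | all 4 rest on readings after anaesthetic |
| 7.1.6 at one visit only | 4 of 8 | all 4 mix the two conditions |
| 7.1.6 at both visits | 8 of 8 | all 4 meet 7.1.6, but the 6.1 order is broken twice |

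The Main Eye summary (SAP 8.2) therefore has 8 readings at issue per LASIK patient. A second study eye adds 8, summarised separately. An early termination visit uses the Week 8 list, but SAP 7.1 may reassign it to another visit, so its readings need not enter the Week 8 summary.

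**5. What cannot be computed.** Eligibility rests on "History of cataract or refractive corneal surgery in the study eye(s) in the previous 6 months" and sets no number or share of LASIK patients. The duration and size of the anaesthetic effect are not stated. No trial total and no attenuation of the endpoint can be derived.

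**6. Where confocal microscopy could go.** It is now separated from the co-primary NEI staining (step 8) by 10 + 5 + 10 = 25 minutes of breaks, plus TFBUT and Cochet-Bonnet. Placed between steps 7 and 8, it could leave a single ten-minute break between anaesthetic and gel and the staining.

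**The case against.** The strongest case on the other side is that harm is not shown. The count above is a count of readings and not an effect size. Fifteen minutes of breaks plus TFBUT come between the tests, and the documents do not allow a judgement on whether any anaesthesia remains at step 7. The endpoint is secondary and descriptive, in a study that the SAP calls exploratory (SAP 8.1). All of this stands. It limits the weight of the point but does not remove the contradiction.

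Three stronger readings are tempting, and the documents do not support them.

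- A reader might infer bias in favour of one arm. The order is the same in both arms of a randomised, masked trial, so nothing points to a shift in one direction.
- A reader might infer that the affected readings would be lost from view in the analysis. The blind data review considers protocol deviations and their consequences for the analysis (SAP 6.1), and all deviations are listed (SAP 9.2). Previous LASIK is recorded by patient and eye (SAP 7.2.3) and listed (SAP 9.3.2), and individual sensitivity readings appear in Listing 16.2.6-2.3. LASIK patients' readings can be identified. What is missing is a pre-specified split.
- A reader might infer that the site changes order between visits. The middle row of the table is only a possibility. This is a single centre, and nothing in the documents indicates that it happens.

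**Conclusion.** The contradiction holds. In LASIK patients, at Baseline and at Week 8/early termination, Protocol 6.1, 7.1, 7.1.6 and 7.1.8 cannot all be followed. If 6.1 is followed, every scheduled aesthesiometry reading in these patients breaches 7.1.6.

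The consequence is limited to one secondary endpoint, analysed descriptively, in LASIK patients only. The likely harm is noise or lost sensitivity to change, of unknown size. SANDE is the first step at each visit and is unaffected, as is the sample size. The conclusion rests on reading 7.1.6 literally and on 7.1 making 6.1 the governing order; both are explicit. It assumes nothing about how long the anaesthetic acts. It is worth correcting because the correction is cheap, and it does not threaten the trial's main conclusions.

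**What to change.** Amend the Baseline and Week 8/early termination lists in Protocol 6.1 in one of two ways.

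- **Preferred: place confocal microscopy last, after NEI staining.** No anaesthetic or gel then precedes Cochet-Bonnet or the co-primary staining. The downside is that fluorescein is instilled before imaging.
- **Alternative: move Cochet-Bonnet to before confocal microscopy.** The downside is that the filament touches the cornea before TFBUT. Confocal microscopy also stays ahead of TFBUT and staining, as it is now.

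Confocal microscopy should not go between Cochet-Bonnet and NEI staining, because anaesthetic and gel could then come directly before a co-primary assessment. Either permitted change moves one line in two lists and adjusts the breaks, with no new procedure or visit.

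If data were already collected:

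1. Check the actual order in source records where it was recorded. No passage requires order or time to be recorded, so this may not always be possible.
2. Handle readings taken after anaesthetic as protocol deviations in the blind data review (SAP 6.1, 9.2).
3. Flag those readings in Tables 14.2-6.1 and 14.2-6.2, or show them separately.
4. If LASIK status has to stand in for test order, say so in the tables, and state that such a split cannot separate an anaesthetic effect from surgery type.

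The cost is a source check for LASIK patients and some smaller groups in two descriptive tables.

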## Study Schedule

Study procedures	Baseline Visit (Day 0)	Week 4 (Day 28±2)	Week 8** (ETV) (Day 56±2)	Week 12 (Follow-up Visit) (Day 84±2)
Informed Consent	X			
Inclusion/Exclusion Criteria	X			
Urine Pregnancy Test	X	X	X	
Randomization	X			
Demographics	X			
Ocular and General Medical History	X			
Previous and Concomitant Ocular And Systemic Medications	X	X	X	X
Frequency of artificial tear use	X	X	X	X
Record Adverse Events (AEs)	X	X	X	X
Verify patient study medication dosing compliance		X	X	
SANDE questionnaire	X	X	X	X
Best Corrected Distance Visual Acuity (BCDVA)	X		X	X
Cochet-Bonnet aesthesiometry	X		X	
External Ocular Examination	X	X	X	X
Slit Lamp Examination (SLE)	X	X	X	X
Fluorescein staining (NEI scale)	X	X	X	X
Tear Film Break-up Time (TFBUT)	X	X	X	X
Corneal confocal microscopy*	X		X	
Study drug dispensation	X	X		

* Only for patients who underwent LASIK surgery            ** ETV – Early Termination Visit to be performed according to Visit Week 8 procedures, if premature treatment discontinuation occurs.            Note: Patient diary will be reviewed for potential AEs, and details as applicable            Abbreviations: SANDE - Symptom Assessment In Dry Eye
				

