### **7.1.5 Tear Film Break Up Time (TFBUT)**

TFBUT will be measured by determining the time to tear break-up. The TFBUT will be performed after instillation of 5 µl of 2% sodium fluorescein solution into the inferior conjunctival cul-de-sac of each eye. The patient will be instructed to blink several times to thoroughly mix the fluorescein with the tear film. In order to achieve maximum fluorescence, the examiner should wait approximately 30 seconds after instillation before evaluating TFBUT. With the aid of a slit lamp at 10X magnification using cobalt blue illumination, the examiner will monitor the integrity of the tear film, noting the time it takes to form lacunae (clear spaces in the tear film) from the time that the eye is opened after the last blink. This measurement will be performed within 10 seconds maximum. The TFBUT will be measured twice during the first minute after the instillation of the fluorescein. If the 2 readings differ by more than 2 seconds a third reading is taken.

The TFBUT value will be the average of the 2 or 3 measurements.

Relevant TFBUT findings will be entered in the eCRF.

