3.4 Efficacy and Safety Endpoints

In the study protocol the following study endpoints are specified.

Clinical efficacy and safety parameters will be evaluated at each time point (days 0, 28±2, 56±2 and 28±2 days after discontinuation of treatment) with the following endpoints:

Primary Efficacy Endpoint

- *Change from baseline in Symptom Assessment in Dry Eye (SANDE) scores for severity and frequency assessed at 8 weeks of treatment*

Co-primary Efficacy Endpoint

- *Changes in Cornea vital staining with fluorescein (National Eye Institute (NEI) scales) assessed at week 8*

Secondary Endpoints

- *Changes in SANDE scores (face values) for severity and frequency*
- *Changes in Conjunctival vital staining with fluorescein (NEI scales)*
- *Changes in Tear film break-up time (TFBUT)*
- *Changes in Cochet-Bonnet corneal aesthesiometry*
- *Changes in Nerve count and morphology at scanning laser in vivo corneal confocal microscopy (only patients who had LASIK surgery) – not covered by this SAP.*

Safety Endpoint

- *Incidence and frequency of Treatment-emergent adverse events (TEAEs), assessed throughout the study*

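### In LASIK patients, confocal microscopy with anaesthetic and gel comes before TFBUT and co-primary staining at Baseline and Week 8 only, which risks added noise and visits that are not comparable

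*Protocol*

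**What the plan says.** Protocol 7.1.8 describes the procedure: "In vivo scanning confocal microscopy will be performed bilaterally in the central cornea". It adds: "Prior to the procedure patients will be treated with anesthetic drops and a viscoelastic liquid gel will be applied to the cornea". The gel serves as immersion medium for the microscope lens. The step applies only to patients who had LASIK surgery.

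The visit tables in Protocol 6.1 number the ocular assessments, and Protocol 7.1 fixes the order: "The assessments must always be performed according the sequence detailed in Par 6.1". The Study Schedule marks confocal microscopy at Baseline and Week 8 only, while fluorescein staining and TFBUT are marked at all four visits. Early terminators have the Week 8 procedures.

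SAP 3.4 gives the co-primary endpoint as "Changes in Cornea vital staining with fluorescein (National Eye Institute (NEI) scales) assessed at week 8". TFBUT is a secondary endpoint. The central cornea, where confocal microscopy is done, is one of the five sectors summed into the co-primary score (Protocol 7.1.7, SAP 7.2.7).

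The external examination, slit lamp and Cochet-Bonnet (Protocol 7.1.1, 7.1.4, 7.1.6) must all be done before anaesthetic drops. The TFBUT and staining sections (7.1.5, 7.1.7) set no such condition. Neither document mentions rinsing, gel removal or any special handling of LASIK eyes.

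**The concern.** TFBUT times the break-up of the tear film, and NEI staining grades the corneal surface. In LASIK patients at Baseline and Week 8, both are read after anaesthetic and gel have been put on that surface. Non-LASIK patients never have this exposure, and LASIK patients do not have it at the routine Week 4 and Week 12 visits.

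Three things are at stake:

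- **Week 8 co-primary.** Any procedure effect that varies from one visit to the next adds noise to the staining change in LASIK eyes. The ANCOVA in SAP 8.2 adjusts for treatment, baseline and number of study eyes, but not for type of surgery. Baseline staining also selects the Main Eye when two eyes are treated (SAP 6.1), so noise there can affect which eye is analysed.
- **Visit profile.** In LASIK eyes, Week 4 and Week 12 changes in staining and TFBUT subtract a post-confocal baseline from a value taken without confocal microscopy.
- **LOCF.** A routine Week 4 staining value carried to Week 8 has the same mismatch with its baseline.

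**Working it through.** **Order of assessments (step numbers in Protocol 6.1)**

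| | Baseline | Week 4 | Week 8/ETV | Week 12 |
|---|---|---|---|---|
| Confocal (LASIK only) | 5 | none | 5 | none |
| TFBUT | 6 | 4 | 6 | 5 |
| Cochet-Bonnet | 7 | none | 7 | none |
| NEI staining | 8 | 5 | 8 | 6 |

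Stated breaks after confocal microscopy are 10 minutes before TFBUT, and 10 + 5 + 10 = 25 minutes in total before staining, plus the time the procedures take.

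**The plan's own figure.** For staining, the difference is 3.9 − 2.9 = 1.0, the SD is 2.2, two-sided alpha is 0.05 and power is 80%. The normal formula gives n = 2 × (1.960 + 0.842)² × 2.2² / 1.0² = 76 per arm at 1:1. At 2:1 this becomes 0.5 × 76 × 3 = 114 and 0.5 × 76 × 1.5 = 57, and with 5% dropout 120 and 60. The plan's figures reproduce. By noncentral t, power at 114/57 is 79.6%.

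**Added noise, t-test on change.** Assume a LASIK share f and an independent extra SD e at each of the two gradings in LASIK eyes. Neither is in the documents. The SD of change is then √(2.2² + 2fe²). For f = 30% and e = 1.0 this is √(4.84 + 0.60) = 2.332. Power at 114/57 for a difference of 1.0:

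| LASIK share | e = 0.5 | e = 1.0 | e = 1.5 |
|---|---|---|---|
| 10% | 79.2% | 77.9% | 76.0% |
| 30% | 78.3% | 74.8% | 69.3% |
| 50% | 77.5% | 71.8% | 63.4% |

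**Added noise, planned ANCOVA.** Let s² be the variance of the score at each visit without added noise, and r the correlation between Baseline and Week 8, also an assumption. A change SD of 2.2 requires 2s²(1 − r) = 4.84. The residual variance is (s² + fe²) − (rs²)² / (s² + fe²). The number-of-eyes covariate is taken to explain nothing. With r = 0.5, s² = 4.84:

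- No added noise: 4.84 − 2.42²/4.84 = 3.63, SD 1.905, power 90%.
- f = 30%, e = 1.0: 5.14 − 2.42²/5.14 = 4.00, SD 2.000, power 87%.
- f = 50%, e = 1.5: 5.965 − 2.42²/5.965 = 4.98, SD 2.232, power 78%.

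For r from 0.3 to 0.7, the last case gives 84% to 73%.

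**LOCF.** Planned dropout is 5% of 180 = 9 patients. At an assumed 30% LASIK share, that is 9 × 0.30 = 2.7, or about three patients. It is fewer if some attend the early termination visit, because confocal microscopy is repeated there.

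**The case against.** The case against runs as follows.

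- **No bias between arms.** The order is the same at Baseline and Week 8 in both randomised, masked arms. A constant procedure effect cancels in the change score. In the ANCOVA it may cancel only in part, but what remains is balanced between arms in expectation. This stands. A reader might infer that the order favours one arm at Week 8; the documents do not support that.
- **The breaks may be enough.** Stated breaks total 25 minutes before staining, and no document shows that gel or anaesthetic still matters by then. This stands as a limit on size. Equally, nothing shows that the breaks remove carry-over, and the protocol itself protects three other examinations from anaesthetic drops.
- **The LOCF mismatch is narrow.** Early terminators have the Week 8 procedures. SAP 7.1 then relabels that visit as Week 4, Week 12 or unscheduled by window, so a carried value may have been taken in the same order as Baseline. This stands: only a value from a routine Week 4 visit is mismatched.
- **The stakes are modest.** All testing is exploratory without type I error control (SAP 3.7, 8.2.1.3). TFBUT has no inference (SAP 9.5.3), and Week 4 and Week 12 staining are summarised descriptively (SAP 9.5.2). This stands.
- **Confocal microscopy is not the only prior contact.** Cochet-Bonnet touches the cornea before staining in all patients at the same two visits. This stands, so the visit mismatch in staining is not confined to LASIK patients. A reader might infer that moving confocal microscopy leaves the surface undisturbed at every visit; for staining it does not.

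**Conclusion.** The point holds as a sequencing weakness. In LASIK patients, TFBUT and co-primary staining follow anaesthetic and gel at Baseline and Week 8 but not at routine Weeks 4 and 12, and the plan does nothing to show or limit carry-over beyond the scheduled breaks. For the Week 8 co-primary the risk is extra noise in LASIK eyes. For Weeks 4 and 12, and for routine Week 4 values carried forward, it is a mismatch with the baseline.

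The size cannot be derived from the documents. The t-test range, from 79.6% down to 63.4%, rests on assumed LASIK shares and noise and ignores baseline adjustment. A reader might take 63% as the expected power, but the documents do not support that: at a correlation of 0.5 the ANCOVA keeps 78% in that extreme case, and a middle case loses about three points (90% to 87%). The correlation is itself an assumption. Nor do the documents establish that carry-over occurs; they leave it possible.

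The order also creates a direct conflict. Protocol 7.1.6 requires aesthesiometry before anaesthetic drops, whereas 6.1 puts it after confocal microscopy in LASIK patients.

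**What to change.** In Protocol 6.1, for Baseline and Week 8/ETV, make confocal microscopy the last ocular assessment, after NEI staining. TFBUT and staining are then not preceded by confocal gel or anaesthetic at any visit, and 6.1 agrees with 7.1.6. The Cochet-Bonnet contact before staining remains at these two visits.

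For data collected in the current order, add to the SAP:

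- a supportive co-primary staining analysis that excludes LASIK patients;
- TFBUT summaries shown separately for LASIK and non-LASIK patients.

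LASIK status is already recorded (SAP 7.2.3). Neither output is planned now, since the only efficacy subgroup is one versus two study eyes (SAP 6.2).

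The cost is a protocol amendment that re-orders two visit tables, plus a few extra outputs. It needs no added procedure, visit or staff. There are two downsides. Confocal images, themselves a secondary endpoint, would be taken after fluorescein and aesthesiometry. If recruitment has started, data from before and after the change would differ, so the date of the change should be recorded and patients identified by the order used.
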